14.4 REPORTING AND EXCLUSIONS

14.4.1 Evaluation of Toxicity

All patients will be evaluable for toxicity from the time of their first treatment with rV-PANVACTM and rF-PANVACTM.

14.4.2 Evaluation of Response

All patients included in the study must be assessed for response to treatment, even if there are major protocol treatment deviations or if they are ineligible.

All of the patients who met the eligibility criteria (with the possible exception of those who received no study medication) should be included in the main analysis of the response rate.

All conclusions should be based on all eligible patients. Subanalyses may then be performed on the basis of a subset of patients, excluding those for whom major protocol deviations have been identified (e.g., early death due to other reasons, early discontinuation of treatment, major protocol deviations, etc.). However, these subanalyses may not serve as the basis for drawing conclusions concerning treatment efficacy, and the reasons for excluding patients from the analysis should be clearly reported. The 95% confidence intervals should also be provided.

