1 OBJECTIVES

1.1 PRIMARY OBJECTIVE

1.1.1 To determine if there is an improvement in disease-free survival (DFS*) with BCG + PANVAC compared with BCG alone in a phase II study in non-muscle invasive high-grade urothelial carcinoma of the bladder who have failed to respond to intravesical BCG. *within 1 year post treatment

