12.1.1.2 Evaluable for objective response

Only those patients who have biopsy-proven disease present at baseline, have received at least one cycle of therapy (6 or fewer weekly intravesical doses of BCG), and have had their disease re-evaluated will be considered evaluable for response. These patients will have their response classified according to the definitions stated below.

In order to compare the secondary outcomes between study arms, all durations will be measured from the start of TICE BCG therapy (week 3). This is the start of therapy for the TICE BCG arm alone. BCG is not started at week 0 for two reasons: 1) to allow adequate healing from previous TURBT and 2) allow vaccinia priming vaccine to be given to combination group at week 0 with enough recovery time to possibly make the administration of BCG in week 3 safer in these patients. Furthermore, by following this schema, patients in each group will start BCG at the same time after study entry.

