12.1.1.3 Recurrence-free survival

The recurrence-free survival duration will be measured from the start of TICE BCG therapy (week 3) until disease recurrence or death due to any cause in each arm. Recurrence is suspected and/or determined by urine cytology and/or cystoscopic exam and then confirmed pathologically after a TURBT. Positive cytology in the absence of pathologic confirmation is not considered to be a recurrence.

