14 STATISTICAL CONSIDERATIONS

14.1 PRIMARY ENDPOINT, STRATIFICATION, AND SAMPLE SIZE JUSTIFICATION

The study is to test the hypothesis that patients in the TICE BCG+PANVAC arm have better recurrence-free survival than patients in the TICE BCG alone arm. Patients to be accrued to the study are adults with high grade non-muscle invasive bladder cancer who failed at least 1 induction course of BCG. These patients comprise 3 subgroups, namely, BCG persistent with one failure of BCG induction course, BCG persistent with 2 or more failures of BCG induction courses, and BCG relapsing that can behave like BCG naïve. The ratio of the composition of the three subgroups is expected to be 1:5:1 with the majority of the patients being BCG persistent and having failed 2 or more BCG induction courses. In order to achieve the balance of treatment in each subgroup, stratified randomization will be implemented in this study. However, although the three subpopulations have different recurrence-free survival experience and may respond to treatment benefit differently, the study is powered to test the overall treatment benefit of BCG+PANVAC on the entire patient population.

In the first subgroup of BCG persistent patients with one failure of BCG induction course, it is assumed that the 1-year recurrence-free survival rate is 37.5% ^{7,8} in the TICE BCG alone arm and 65% in the TICE BCG+PANVAC arm.^{38,39} Under the assumption of exponential distribution for the recurrence-free survival in both arms, the difference in recurrence-free at 1-year corresponds to hazard ratio (HR) of 2.277. In the second subgroup of BCG persistent patients with 2 or more failures of BCG induction courses, the 1-year recurrence-free survival rate in the TICE BCG alone arm is expected to be 20%.⁴⁰ Assume that the treatment benefit of TICE BCG+PANVAC in the second subgroup is lower than in the first subgroup and HR is set at 2, which corresponds to a one-year recurrence-free survival of 44.7% in the TICE BCG+PANVAC arm. In the third subgroup of BCG relapsing patients, it is expected that the 1-year recurrence-free survival rate is 48% and 65% in the TICE BCG alone and TICE BCG+PANVAC arm, respectively. This corresponds to HR=1.70.

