Patient accrual is targeted at one patient per month during the first 6 months and 2 patients per month afterwards, and follow-up period after completing accrual will be 12 months. The power calculation was based on one-sided log-rank test at 15% significance level. Sample size, power and duration of the study are presented in the table below. With a total number of 49 patients, the power is 84% (see table below). Under this scenario, the expected number of events (recurrence or death) is 40. In order to allow for the possibility of a small number of unevaluable patients, the accrual ceiling will be set at 54 patients.

	Subgroup 1 1-year recurrence-free survival for BCG persistent patients who failed 1 BCG induction course	Subgroup 2 1-year recurrence-free survival for BCG persistent patients who failed 2 or more BCG induction courses	Subgroup 3 1-year recurrence-free survival for BCG naïve patients	Total sample size	Power (%)	Duration of accrual (months)	Expected number of events (recurrence or death)
Treatment benefit	HR=2.277 1-year RFS: BCG alone: 37.5% BCG+PANVAC: 65%	HR=2 1-year RFS: BCG alone: 20% BCG+PANVAC: 44.7%	HR=1.7 1-year RFS: BCG alone: 48% BCG+PANVAC: 65%	49	84	28	40

One interim analysis for futility will be performed according to the stopping procedure.³⁹ Specifically, the interim analysis will be performed when half of the expected events (20) have been observed. At that time, if the observed event rate of the TICE BCG+PANVAC arm is higher than that of the TICE BCG alone arm (i.e. the hazard ratio ≥ 1), we would consider terminating the trial and concluding that an advantage for the BCG+PANVAC regimen has not been established.

For the purpose of protecting patient safety, we implement the following stopping rule for safety monitoring of patients who receive the combination therapy.

If one patient experiences a grade 5 event, thought to be possibly or probably due to the combination therapy, the study will be stopped. For grade 3 or 4 event, the study will be stopped according to the following stopping rule. These adverse events are described in more detail in Section 7.

Number of patients	No. of grade 3 or 4 serious adverse events
3-9	3
10-18	4
19-26	5

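### The deciding endpoint carries three labels (1-year DFS, RFS, response rate); only the RFS log-rank test has a calculation behind it, and its 84% power and 40 events need follow-up beyond 1 year per patient

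*Combined protocol and SAP*

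**What the plan says.** Four places bear on which result decides efficacy.

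- **Précis and Section 1.1.1.** The primary objective is "To determine if there is an improvement in disease-free survival (DFS*) with BCG + PANVAC compared with BCG alone", with the footnote "within 1 year post treatment". DFS has no definition, time origin or test of its own. The précis attaches the 84% power, one-sided 0.15 and 49 subjects to this DFS wording.
- **Section 14.1**, headed as the primary endpoint section. The hypothesis is that "patients in the TICE BCG+PANVAC arm have better recurrence-free survival than patients in the TICE BCG alone arm". On the test it says "The power calculation was based on one-sided log-rank test at 15% significance level", giving 84% power with 49 patients and 40 expected events.
- **Section 12.1.** Section 12.1.1.3 reads "The recurrence-free survival duration will be measured from the start of TICE BCG therapy (week 3) until disease recurrence or death due to any cause", with no time limit. Section 12.1.1.2 presents the common week 3 origin as a means of comparing secondary outcomes. It also says of response: "These patients will have their response classified according to the definitions stated below". Only RFS, PFS and time to recurrence follow.
- **Section 14.4.2.** Patients who met the eligibility criteria "should be included in the main analysis of the response rate". It then says that conclusions rest on all eligible patients.

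Two follow-up statements also matter. Section 14.1 assumes 12 months of follow-up after accrual completes. Sections 5.7 and 5.8.2 end each patient's follow-up 1 year after the 20-week course or after treatment.

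**The concern.** A reader who starts from the objective, from Section 14.1 or from Section 14.4.2 arrives at a different named endpoint. Section 14.1 describes the log-rank test as the basis of the power calculation, but no sentence says it is the one analysis that decides efficacy. The explicit commitment to compare arms by log-rank, in Section 14.2, covers secondary endpoints.

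Two things are at stake. First, the stated power and event count belong to one reading only, and the 1-year limit in the objective is not that reading. Second, this is an open-label trial of 49 patients tested at a lenient 15% level. If the horizon or endpoint is settled after results are seen, even that level is not held.

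**Working it through.** **Inputs (Section 14.1 unless noted).** 49 patients; 1:1 allocation (Section 4.3); subgroup mix 1:5:1, taken as 7, 35 and 7; 1-year RFS on BCG alone 37.5%, 20% and 48%; hazard ratios (control over combination) 2.277, 2 and 1.7; exponential times; accrual of 1 per month for 6 months, then 2 per month; analysis 12 months after the last accrual; one-sided 0.15, so the critical z is 1.036. Dropout and the futility look are not modelled.

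**Step 1: reproduce the stated design.**
- Accrual time: 6 + 43/2 = 27.5 months (stated 28). The cut-off is 27.5 + 12 = 39.5 months.
- Monthly control hazards are −ln(S)/12: 0.0817, 0.1341 and 0.0612. Each is divided by its hazard ratio for the combination arm.
- Expected events: sum 1 − exp(−hazard × follow-up) over patients, averaged over arms and the 1:5:1 mix. Result: 39.7 (stated 40).
- Freedman power at the average hazard ratio 1.99: √40 × (1.99 − 1)/(1.99 + 1) − 1.036 = 2.095 − 1.036 = 1.06, which is 85.5%.
- Simulated unstratified log-rank power (20,000 trials): 85%.

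The stated 84% and 40 events therefore reproduce, for the RFS log-rank test with follow-up to the common cut-off. On that schedule the earliest patients are followed for about 39 months.

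**Step 2: apply a 1-year limit to each patient.** The footnote does not fix its starting point, so two readings bound the range: 12 months from first BCG, and 1 year after week 20. The second is study week 72, or 72 − 3 = 69 weeks from first BCG, about 15.9 months.

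| RFS log-rank test | Expected events | Power | Disagrees with uncapped test, plan's effect |
|---|---|---|---|
| To 12 months after last accrual | 39.7 | 85% | – |
| Capped 1 year after week 20 | about 34 to 35 | 82 to 83% | about 7% |
| Capped 12 months from first BCG | about 30 | 79% | about 11 to 12% |

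Disagreement means that one test is significant and the other is not.

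**Step 3: error rate if either horizon could be used.** With no treatment effect, the uncapped test alone rejects in about 0.14 of trials. Allowing a claim on either the uncapped or a capped test gives 0.17 (cap 1 year after week 20) to 0.18 (cap 12 months from first BCG).

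**Step 4: the objective read as a 1-year proportion.** The mixed rates are (37.5 + 5 × 20 + 48)/7 = 26.5% and (65 + 5 × 44.7 + 65)/7 = 50.5%. A two-proportion test at one-sided 0.15 with 24.5 per arm has about 76% power. It would need 33 per arm, 66 in total, for 84%.

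**Step 5: response rate.** This cannot be calculated from the documents, because no response rate is defined. As an illustration only, if it meant tumour-free status at about 3.5 months from first BCG (the week 17-20 evaluation), power would be about 58%.

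**The case against.** The strongest reply is that the plan has one endpoint under loose labels. Section 14.1 carries the primary endpoint heading, names RFS, and gives its test basis, alpha, event count and an event-driven futility look. The précis states the same hypothesis with DFS in place of RFS, and the same power, alpha and sample size. Section 5.2.2.3 treats recurrence as the primary endpoint. Response rate appears in no objective and nowhere in Sections 14.1 to 14.3. The sentence in Section 14.4.2 sits under reporting and exclusions, says who is included, and compares no arms.

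Most of this stands. DFS is probably RFS under another name, and the response-rate sentence reads as general text. A reader might infer that the plan sets up three rival deciding tests that can give opposite answers. The documents do not support that: only the RFS log-rank test is specified as a comparison. The disagreements are also in significance, and reversals of direction are rare (about 1 to 2% of trials for the capped tests under the plan's effect).

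What the reply does not remove is the horizon. The objective has a 1-year limit, the RFS definition has none, and the 40 events need follow-up that Sections 5.7 and 5.8.2 do not provide. Nor does it make the response-rate sentence harmless, since Section 14.4.2 calls that the main analysis and goes on to govern efficacy conclusions.

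**Conclusion.** The labelling is inconsistent and should be corrected. The measurable consequence is moderate. Depending on where the 1-year limit starts, the trial as described yields about 30 to 35 events and 79 to 83% power, not 40 and 84%. An unsettled choice between capped and uncapped analysis moves the one-sided error from about 0.14 to 0.17-0.18.

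These figures rest on the plan's own rates, accrual and exponential assumption, with no dropout and no futility look. The error figure applies only if a claim on either horizon is allowed. No section permits that, and none rules it out.

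A reader might go further and cite 58% power, disagreement in about a third of trials, or an overall error of 27 to 28%. Those figures assume that response means tumour-free status at weeks 17-20, and the last also assumes that success may be claimed on any of three tests. Neither assumption is in the documents, so they should not be used to size this point.

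**What to change.** 1. **Section 14.4.2:** replace the reference to a main analysis of response rate with the primary analysis of recurrence-free survival described in Section 14.1.
2. **Précis, Sections 1.1.1 and 14.1:** use one label, RFS, with one start (first BCG, week 3) and one stated time horizon. Reconcile the 1-year limit in the objective and the 1-year off-study rule with the follow-up that produces 40 events. If the 1-year limit is kept, restate events and power. Do not simply substitute the Section 12.1.1.3 definition, because that would delete the only horizon the objective has.
3. **Section 14.1:** state that the one-sided 15% log-rank test of RFS is the sole test deciding efficacy. The 1-year rate and tumour-free status at weeks 17-20 are then descriptive.
4. **Section 12.1.1.2:** say that the common time origin serves primary and secondary outcomes.

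The cost is wording, with no new patients or visits. A favourable 1-year or response rate could no longer carry the efficacy conclusion, and the stated power may become slightly less favourable. Section 8 records closure with CTEP on 5/1/2019 and the current version is dated 05/22/2025, so the amendment should record that it clarifies the endpoint and whether outcome data had been seen.

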15 HUMAN SUBJECTS PROTECTIONS

15.1 RATIONALE FOR SUBJECT SELECTION

15.1.1 Selection Based on sex, Ethnicity, and Race

Subjects from all racial/ethnic groups and both sex are eligible for this study if they meet the eligibility criteria. To date, there is no information that suggests that differences in drug metabolism, immune response or disease response would be expected in one group compared with another. Efforts will be made to extend accrual to a representative population, but in this preliminary study, a balance must be struck between patient safety considerations and limitations on the number of individuals exposed to potentially toxic and/or ineffective treatments on one hand and the need to explore sex and ethnic aspects of clinical research on the other hand. If differences in outcome that correlate with ethnic identity are noted, accrual may be expanded or a follow-up study may be written to investigate those differences more fully.

15.1.2 Justification for Exclusions

Due to impaired cellular immunity, HIV patients are at an increased risk of serious side effects from vaccinations with infectious agents and are excluded. This is based on recommendations from the CDC and FDA. In addition, pregnant women are also excluded due to potentially increased risks of serious side effects from vaccinations with infectious agents.

15.2 PARTICIPATION OF CHILDREN

Individuals under the age of 18 will not be eligible for participation in this study based on the fact that patients under 18 are unlikely to have this disease and there are unknown toxicities in pediatric patients.

15.3 PARTICIPATION OF SUBJECTS UNABLE TO GIVE CONSENT

Adults unable to give consent are excluded from enrolling in the protocol. However re-consent may be necessary and there is a possibility, though unlikely, that subjects could become decisionally impaired. For this reason and because there is a prospect of direct benefit from research participation (section 15.5), will be offered the opportunity to fill in their wishes for research and care, and assign a substitute decision maker on the “NIH Advance Directive for Health Care and Medical Research Participation” form so that another person can make decisions about their medical care in the event that they become incapacitated or cognitively

impaired during the course of the study. Note: The PI or AI will contact the NIH Ability to Consent Assessment Team for evaluation. For those subjects that become incapacitated and do not have pre-determined substitute decision maker, the procedures described in MEC Policy 87-4 for appointing a surrogate decision maker for adult subjects who are (a) decisionally impaired, and (b) who do not have a legal guardian or durable power of attorney, will be followed.

Participating sites should adhere to appropriate procedures specific to their site.

15.4 EVALUATION OF BENEFITS AND RISKS/DISCOMFORTS

BCG is a standard of care treatment and will be used in this study. The biggest risk of using this agent after failing an initial induction course of BCG is progression of disease to muscle-invasive disease. However, this occurs after multiple, failed BCG induction treatments and occurs more often after 2 years of such therapy⁴⁰. In addition, patients will be accurately staged for disease with imaging, TURBT, and in some cases, repeat TURBT. They will be followed quite rigorously throughout the study and thereafter with a planned biopsy between weeks 17-20 to ensure that no progression of disease has occurred during the treatment period. Patients who progress will promptly undergo radical cystectomy. Radical cystectomy and pelvic lymphadenectomy is also considered a standard of care treatment for high grade BCG refractory NMIBC. However, since enrollment into this study requires patients to refuse radical surgery or not be medically fit for surgery, we believe the risk of proceeding with another induction course of BCG is outweighed by its benefit.

Other risks of the use of BCG include local bladder symptoms such as blood in the urine, urinary frequency, urgency of urination, dysuria (pain), and bladder spasms which are often self-limiting and usually resolve within a week by withholding BCG and administering standard of care medications (e.g. anti-inflammatories, anti-spasmodics, hydration, etc.). Finally, a rare potential risk of BCG administration is development of “BCG-osis” which is a form of bacteremia/urosepsis or systemic BCG infection that occurs with BCG administration on very rare occasions. In this event, patients will be taken off the study and treated with anti-microbials as per recommendations by infectious disease consultants. The addition of PANVACTTM is unknown but given the relative safety of both agents and different routes of administration, we presume that the risk is minimal.

15.4.1 Alternative Approaches or Treatments

Patients will be consented verbally and in writing regarding the risks and benefits of this trial, the treatment requirements, and alternative approaches to entering on this trial.

15.4.2 Procedure for Protecting Against or Minimizing any Potential Risks

All care will be taken to minimize side effects, but they can be unpredictable in nature and severity. This study may involve risks to patients, which are currently unforeseeable. All patients will have blood tests, examinations and CT scans of the chest/abdomen/pelvis as described in the monitoring schedule as described in Appendix C (Section 17.3). Patients will also be required to have a local physician to provide long-term care and to monitor for complications. If patients suffer any physical injury as a result of the participation in this study, immediate medical treatment is available at the Warren Grant Magnuson Clinical Center, Bethesda, Maryland. Although no compensation is available, any injury will be evaluated and

treated in keeping with the benefits or care to which patients are entitled under applicable regulations.

15.4.3 Provisions for Monitoring Data Collection to Ensure Safety of Subjects

As information is gathered from this trial, clinical results will be shared with patients. Laboratory and clinical data will be frequently gathered and any new significant finding(s) found during the course of the research, which may affect a patient's willingness to participate further, will be explained. Confidentiality of information concerning participants will be maintained, including in all publications and presentations resulting from this study. Names of participants or material identifying participants will not be released without permission, except as such release is required by law. Records at the Clinical Center are maintained according to current legal requirements, and are made available for review by Cancer Therapy Evaluation Program, the Food and Drug Administration, or other authorized users, as stated under the guidelines established by the Federal Privacy Act.

15.5 RISKS/BENEFITS ANALYSIS

The patients we will be enrolling have high grade NMIBC that has already failed the standard of care therapy, BCG induction. These patients are on the verge of developing muscle-invasive disease which requires potentially morbid surgery and change in quality of life. Therefore, they are very interested in strategies to preserve the bladder. Repeat induction BCG therapy is a standard of care and is being given to all patients in this study. The addition of PANVAC™ may potentially improve upon the poor RFS seen with BCG alone and hopefully this study will bear that out. Alternative treatments besides surgery include other intravesical agents that have not shown to be that effective. Whether the vaccine will have any clinical effect upon improving the outcome with BCG is unknown, therefore, benefit cannot be promised nor can the chance of benefit be accurately predicted. Patients' participation in this study is voluntary and refusal will not result in penalty or loss of benefit to which patient is otherwise entitled.

Participation may be discontinued at any time without penalty and the patient can ask questions.

